## ABBREVIATIONS AND DEFINITIONS

Abbreviation	Definition
6MWD	6-Minute Walk Distance
6MWT	6-Minute Walk Test
AE	Adverse Event
ALT	Alanine Aminotransferase
AST	Aspartate Aminotransferase
BUN	Blood Urea Nitrogen
cMRI	Cardiac Magnetic Resonance Imaging
CPET	Cardiopulmonary Exercise Testing
CSR	Clinical Study Report
DSMB	Data Safety Monitoring Board
ECG	Electrocardiogram
eCRF	Electronic Case Report Form
ERA	Endothelin Receptor Antagonist
IQR	Interquartile Range
IV	Intravenous(ly)
LOCF	Last Observation Carried Forward
LV	Left Ventricular
LVEDP	Left Ventricular End-Diastolic Pressure
LVEF	Left Ventricular Ejection Fraction
MedDRA	Medical Dictionary for Regulatory Activities
NT-proBNP	N-Terminal Pro-Brain Natriuretic Peptide
PAH	Pulmonary Arterial Hypertension
PDE5-I	Phosphodiesterase Type 5 Inhibitor
PedsQL	Pediatric Quality of Life Inventory
PK	Pharmacokinetic(s)
PT	Preferred Term
QOL	Quality of Life
RV	Right Ventricular
RVEDV	Right Ventricular End-Diastolic Volume
RVEF	Right Ventricular Ejection Fraction
SAE	Serious Adverse Event
SAP	Statistical Analysis Plan
SC	Subcutaneous
SD	Standard Deviation
sGC	Soluble Guanylate Cyclase
SOC	System Organ Class
TEAE	Treatment-emergent Adverse Event

Abbreviation	Definition
TID	Three Times Daily
UTC	United Therapeutics Corporation
$VCO_2$	Carbon Dioxide Output
VE	Minute Ventilation
$VO_2$	Oxygen Uptake
WHO	World Health Organization
WHODD	World Health Organization Drug Dictionary

### 1 PREFACE

This statistical analysis plan (SAP) provides further details of the planned analyses for the TDE-PH-206 study, as presented in the original protocol, dated 29 July 2014, and subsequent amendments. The purpose of this SAP is to ensure that the statistical methodologies that will be used, and the data listings, summary tables, and figures which will be produced, are appropriate and complete to support valid conclusions regarding the study objectives and the completion of the clinical study report (CSR). Additional post-hoc or unplanned analyses, which are not defined in this SAP, may be performed to support the clinical development program. Such analyses will be documented in the CSR.

### 2 STUDY OBJECTIVES AND ENDPOINTS

## 2.1 OBJECTIVES

## 2.1.1 Primary Objective

To assess the safety and tolerability of oral treprostinil extended release tablets in 3 cohorts of pediatric subjects with pulmonary arterial hypertension (PAH) aged 7 to 17 years:

- Cohort 1: Subjects transitioning from intravenous (IV) or subcutaneous (SC) Remodulin
- Cohort 2: Subjects transitioning from inhaled prostacyclin
- Cohort 3: As add-on to current PAH therapy in de novo prostacyclin subjects

## 2.1.2 Secondary Objective

- 1. To assess the effect of oral treprostinil on the following (assessed in all cohorts):
  - Cardiopulmonary exercise testing (CPET) with progressive cycle ergometry
  - Symptoms of PAH

- Panama and World Health Organization (WHO) Functional Classification
- 6-minute walk distance (6MWD) (with pulse oximetry and heart rate recovery monitoring)
- Borg dyspnea score
- Quality of life (QOL) assessed via the Pediatric Quality of Life Inventory (PedsQL) questionnaire
- Plasma N-terminal pro-brain natriuretic peptide (NT-proBNP)
- Cardiac magnetic resonance imaging (cMRI)
- 2. To describe treprostinil pharmacokinetics (PK) in pediatric subjects with PAH aged 7 to 17 years.

### 3 STUDY DESIGN

This is a multicenter, open-label, safety and tolerability study of oral treprostinil administered 3 times daily (TID) (approximately every 8 hours with adjustments permitted based on the subject's lifestyle and schedule, but not sooner than every 6 hours) in pediatric PAH subjects 7 to 17 years of age (1) transitioning from continuous IV/SC Remodulin, (2) transitioning from inhaled prostacyclin, or (3) as add-on to current PAH therapies in de novo prostacyclin subjects. Eligible subjects will be assigned to a cohort based upon their PAH therapy at the time of enrollment.

Up to 7 study visits will occur during the 24-week study at the following time points: Screening, Baseline, Weeks 0 (Cohort 1 only; in-patient hospital stay Days 1 to 5), 3, 6, 12, and 24.

## Cohort 1 Subjects

Following completion of Baseline assessments, including an 8-hour PK assessment while receiving IV/SC Remodulin within 7 days prior to the first dose of oral treprostinil, subjects in Cohort 1 will undergo an inpatient hospital stay lasting approximately 5 days to transition from IV/SC Remodulin to oral treprostinil. The target transition goal is 5 days and for the subject to be completely transitioned off IV/SC Remodulin prior to discharge from the hospital. Subjects will be discharged from the hospital after they have transitioned off IV/SC Remodulin, reached their target oral treprostinil dose, or as the Investigator deems appropriate. If necessary or if appropriate per Investigator discretion, subjects can prolong or complete the transition in an outpatient setting for a total transition time of up to 4 weeks.

The maximum time to titrate off IV/SC Remodulin is 4 weeks from the start of the transition; if the subject is not fully transitioned by Week 4, they will be removed from the study. If the subject is in the hospital during one of the scheduled study visits, the assessments for that visit will be conducted as scheduled during the defined visit window.

## Cohort 2 and 3 Subjects

Following completion of Baseline assessments, the first dose of 0.125 mg oral treprostinil should be taken at the study site. Dosing of oral treprostinil will be initiated at 0.125 mg TID with food (approximately every 8 hours with adjustments permitted based on the subject's lifestyle and schedule, but not sooner than every 6 hours). Dose changes should be conducted under appropriate medical supervision in consultation with the study site.

## Dose Optimization/Evaluation Phase for ALL Cohorts

Week 3, Week 6, and Week 12: Subjects will return to the clinic for the following assessments: vital signs, 6-minute walk test (6MWT)/Borg dyspnea score, Panama and WHO Functional Classification, symptoms of PAH, and safety assessments. At each visit, females of childbearing potential will undergo a urine pregnancy test. At Week 12, QOL (as measured by PedsQL questionnaire) and clinical laboratory assessments, including NT-proBNP testing, will occur.

Week 24 (or premature discontinuation): Subjects will return to the clinic for the following assessments: vital signs, physical examination, 6MWT/Borg dyspnea score, CPET, Panama and WHO Functional Classification, symptoms of PAH, QOL assessment, NT-proBNP, cMRI, clinical laboratory assessments, electrocardiogram (ECG), and safety assessments. Females of childbearing potential will undergo a urine pregnancy test. In addition, all subjects will undergo an 8-hour PK assessment.

### 4 RANDOMIZATION

No randomization will occur. All subjects will receive treatment with oral treprostinil. Subjects will be enrolled into a cohort based on their current PAH treatment regimen.

## 5 SEQUENCE OF PLANNED ANALYSES

A Data Safety Monitoring Board (DSMB) will meet after 5 subjects have enrolled in Cohort 1 and transitioned from IV/SC Remodulin to evaluate any safety concerns. The safety data will be prepared according to the separate DSMB analysis plan. The IV/SC Remodulin dose will be 25 to 75 ng/kg/min, inclusive, for the first 5 subjects enrolled in Cohort 1. Following the DSMB safety review, the dose range may be expanded to 25 to 125 ng/kg/min, inclusive, for the remaining subjects.

Additionally, if 2 or more of the first 5 subjects within any cohort meet the pre-specified stopping criteria, the DSMB will review the data prior to enrolling additional subjects into that cohort.

Analysis of PK samples may be performed, as warranted, to guide dosing.

Upon completion of all study subjects, after all outstanding queries are resolved and all data management quality assurance procedures are completed, the database will be locked. All data from the electronic case report form (eCRF), as well as data transmitted from external vendors for laboratory and PK presentation, will be included in the locked database. All final analyses will be performed on the final locked database.

### **6** SAMPLE SIZE CONSIDERATIONS

This study is intended to provide descriptive data only. A sample size of 40 subjects (25 transition [IV/SC Remodulin and inhaled prostacyclin] subjects and 15 de novo subjects) was selected for feasibility and to provide a reasonably large experience base with which to draw conclusions about the safety of the proposed protocol for (1) transition from moderate to high doses of IV/SC Remodulin to oral treprostinil, (2) transition from inhaled prostacyclin to oral treprostinil, and (3) initiation of oral treprostinil as add-on therapy in de novo prostacyclin subjects. No formal sample size computation was performed with respect to the primary objective of evaluating safety and tolerability, as only descriptive reporting of safety data is planned. The planned sample size of 10 to 15 subjects within a cohort is appropriate for further characterization of the safety, PK, and clinical benefit of oral treprostinil in this pediatric subject population with PAH.

## 7 ANALYSIS POPULATIONS

The Safety population will include all subjects who receive at least 1 dose of oral treprostinil.

The PK population will include all subjects who receive at least 1 dose of oral treprostinil and who provide adequate PK samples to estimate the treprostinil PK parameters. A subject's status in the PK population will be determined by the PK analysis and report writing vendor, and provided to United Therapeutics Corporation (UTC) electronically.

### 8 GENERAL CONSIDERATIONS FOR DATA ANALYSES

All of the data included in the final locked database will be listed. In general, listings will be sorted by cohort, subject, and scheduled assessment (if applicable). Listings will include assessment date, assessment time (if available), and study day. For data collected on a fixed schedule, the assessment identifier will also be included on the listing.

In general, the data will be summarized by scheduled assessment (if applicable). For continuous variables, the summary statistics will include number of subjects, mean, standard deviation (SD), median, minimum, and maximum.

Minimums and maximums will be expressed using the level of precision in which the variable was collected. All other statistics will be rounded, using an additional decimal point. For discrete variables, summaries will include the frequency and percentage in each category. Percentages will be rounded to 1 decimal point. Whenever practical, categories of discrete variables will be ordered and labeled as they appear in the eCRF, and all categories represented on the eCRF will be included in summaries, even when they do not apply to any subjects in the study.

### 8.1 PREMATURE DISCONTINUATION AND MISSING DATA

Subjects may not complete the treatment period for a number of reasons, including but not limited to voluntary withdrawal, stopping criteria met, serious or life-threatening adverse event (AE), protocol deviation, behavior likely to undermine the validity of results, or pregnancy.

All available data from all safety subjects will be used as detailed in this SAP. Subjects will contribute the data available up to the point of study completion, or study discontinuation for any reason.

## 8.2 MULTIPLE COMPARISONS AND MULTIPLICITY

No adjustment for multiple comparisons will be made in these analyses, as no formal hypotheses are being tested.

### 9 STUDY POPULATION

### 9.1 SUBJECT ACCOUNTABILITY

The listing of discontinued subjects will include all subjects who discontinued the study prematurely and will include cohort number, subject number, analysis population inclusion, date/time of last oral treprostinil dose, date subject discontinued from study, and reason for study discontinuation.

The listing of subject accountability will include all subjects who were screened for study participation. This listing will include cohort number, subject number, analysis population inclusion, informed consent date, enrollment status, reason for screen failure (if applicable), date subject completed or discontinued from study, completion status, reason for study discontinuation (if premature), whether subject was able to transition to oral treprostinil, and reason subject was unable to transition (is applicable). Any stopping criteria met will also be listed for each subject.

A listing of subjects excluded from the PK analysis will include cohort and subject number.

The number of subjects who were screened, failed screening (along with reasons for screen failure), enrolled in the study, included in the Safety population, included in the PK population, discontinued from study prematurely (along with reasons for premature discontinuation), and died during the study will be summarized by cohort and overall.

## 9.2 ELIGIBILITY CRITERIA

The eligibility criteria not met will be listed for all subjects, along with the date of the initial screening assessment. The listing will include all eligibility criteria not met by criterion

number, as noted in the protocol. If a subject meets all eligibility criteria, the listing will simply be blank for "Criteria not met." A footnote will be added to this listing referring the reviewer to the protocol for exact eligibility criteria language. Entry criteria not met will be summarized by cohort and overall, displaying the number of subjects with at least 1 violation, as well as the specific criterion violated.

### 9.3 PROTOCOL DEVIATIONS

Protocol deviations are collected via a Microsoft Excel spreadsheet outside of the eCRF. The Clinical Trial Lead will provide the final protocol deviation spreadsheet at the conclusion of the study, which will include the subject number, timing of the deviation (visit number), deviation category (i.e., efficacy, safety, PK, informed consent, visit window, etc.), deviation description, and the classification of the deviation (major/minor). A SAS dataset will be created from this spreadsheet and utilitized to create the listing of protocol deviations collected during the study for all subjects.

## 9.4 OTHER DESCRIPTIONS OF STUDY POPULATION

## 9.4.1 Demographics

All demographic data will be listed for the Safety population, including date of birth, age at diagnosis (years), age at enrollment (years), gender, ethnicity, and race. Age at diagnosis requires a calculation using the subject's date of birth and date of initial PAH diagnosis. Age at enrollment is calculated within the eCRF and will therefore be available in the raw datasets. Both ages will be rounded to 1 decimal place. Age at diagnosis, age at enrollment, gender, ethnicity, and race will be summarized by cohort for the Safety population. Age at diagnosis and age at enrollment will be summarized both descriptively and categorically using the age groups 7 to < 12 and 12 to  $\le$ 17 years.

### 9.4.2 PAH History

Pulmonary arterial hypertension history data will be listed, including date of initial PAH diagnosis, years since PAH diagnosis, and current PAH diagnosis. Current PAH diagnosis will be summarized by cohort.

## 9.4.3 Medical History

Medical history data will be coded using the Medical Dictionary for Regulatory Activities (MedDRA) terms. These data and their coded values will be listed, including assessment date and all medical conditions collected. Subjects with no significant medical history will have "None reported" denoted on the listing. The number of subjects with at least 1 medical condition reported will be summarized by cohort, along with the medical conditions by the coded system organ class (SOC) and preferred term (PT). The listing and summary table will include a footnote denoting the MedDRA version used for coding.

## 9.4.4 Prior Therapy

Remodulin medication history data will be listed, including date Remodulin was first initiated, current Remodulin dose, Remodulin route, and date current Remodulin dose was initiated. Inhaled medication history data will be listed, including date Tyvaso first initiated, current number of breaths per session of Tyvaso, current number of sessions per day of Tyvaso, date current Tyvaso dose was initiated, date Ventavis first initiated, current dose of Ventavis per session, current number of sessions per day of Ventavis, and date current Ventavis dose was initiated. Background medication history data will be listed, including use of endothelin receptor antagonist (ERA) (yes/no), use of phosphodiesterase type 5 inhibitor (PDE5-I) (yes/no), use of soluble guanylate cyclase (sGC) stimulator (yes/no), and for each of the medication types, the generic name, date drug was first initiated, current total daily dose, and date current dose was initiated.

The summary of Remodulin medication history will include descriptive statistics on the current Remodulin dose and route for Cohort 1 only. The summary of inhaled medication history will include descriptive statistics of the current number of users, current number of breaths/current dose, and sessions per day for each medication (Tyvaso and Ventavis) by cohort. The summary of background medication history will include descriptive statistics of the current number of users, generic medication names, and current total daily dose for each medication type (ERA, PDE5-I, and sGC stimulator) by cohort.

### 9.4.5 Concomitant Medication

Concomitant medications data will be coded using the World Health Organization Drug Dictionary (WHODD). These data and their coded values will be listed, including medication name, start/end date (or ongoing), condition treated/indication, and AE, if applicable. The number of subjects reporting at least 1 concomitant medication will be summarized by cohort, along with the concomitant medications utilizing the name from the WHODD.

### 10 EFFICACY ANALYSES

All efficacy data will be listed for all enrolled subjects and summarized for all Safety population subjects.

## 10.1 TRANSITION TO ORAL TREPROSTINIL

The safety and tolerability of transitioning subjects from IV/SC Remodulin to oral treprostinil (Cohort 1) or from inhaled prostacyclin (Cohort 2) will be based on the percentage of subjects successfully transitioning to oral treprostinil. A successful transition is defined as a subject from Cohort 1 or 2 who is receiving oral treprostinil and no longer receiving IV/SC Remodulin or inhaled prostacyclin, respectively, at Week 4 and clinically maintained on oral treprostinil treatment through Week 24. A successful initiation of oral treprostinil (Cohort 3) will be defined as a subject who has been clinically maintained on oral treprostinil through Week 24. The number (percentage) of subjects who successfully transitioned to oral treprostinil, as well as those who did not successfully transition to oral treprostinil, will be summarized by cohort and overall. The reasons for unsuccessful transition will also be summarized for those subjects who did not successfully transition to oral treprostinil.

### 10.2 CARDIOPULMONARY EXERCISE TESTING

Cardiopulmonary exercise testing will be completed at Baseline and Week 24 or premature termination. Exercise data will be sent to a central site and analyzed by a centralized specialist. Cardiopulmonary exercise testing entails measurements of oxygen uptake (VO2), carbon dioxide output (VCO2), minute ventilation (VE), and other variables.

The listing of CPET will include the scheduled visit; date/time of assessment; Remodulin, oral treprostinil, Tyvaso, and Ventavis dosing information prior to the CPET assessment, as

applicable; as well as baseline (pre-exercise) and exercise (post-exercise) peak VO2, post-exercise peak watts and VE/VCO2 slope, warm-up duration (minutes), exercise duration (minutes), and reason for test termination.

A summary of CPET will be produced for data collected before the exercise (labelled "baseline" on the CRF) and after the exercise (labelled "exercise" on the CRF), separately. The summary of CPET before exercise will include descriptive statistics for VO2 at Baseline and Week 24 by cohort. The summary of CPET after exercise will include descriptive statistics at Baseline and Week 24 for warm-up duration (minutes), exercise duration (minutes), peak VO2, VE/VCO2 slope, and peak watts. Changes from Baseline to Week 24 in peak VO2, VE/VCO2 slope, and peak watts will also be descriptively summarized. These changes will be compared within cohorts using a paired t-test and p-values will be calculated for descriptive purposes; no formal hypothesis testing is planned. The number (percentage) of subjects reporting reasons for test termination will be summarized categorically (fatigue vs. other) by cohort.

The dosing information prior to testing (number [percentage] of subjects taking each medication type and last dose) will also be summarized by cohort using descriptive statistics.

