Title Study Phase	A Multicenter, Open-Label, 24-Week, Uncontrolled Study to Evaluate the Safety, Tolerability, and Pharmacokinetics of Oral Treprostinil Extended Release Tablets Following Transition from Remodulin or Inhaled Prostacyclin Therapy or as Add-on to Current PAH Therapy in De Novo Prostacyclin Pediatric Subjects Aged 7 to 17 Years with Pulmonary Arterial Hypertension Phase II
Indication	Pulmonary Arterial Hypertension (PAH)
Primary Objective	 To assess the safety and tolerability of oral treprostinil extended release tablets in three cohorts of pediatric subjects with PAH aged 7 to 17 years: Cohort 1: Subjects transitioning from intravenous (IV) or subcutaneous (SC) Remodulin[®] Cohort 2: Subjects transitioning from inhaled prostacyclin Cohort 3: As add-on to current PAH therapy in de novo prostacyclin subjects
Secondary Objective(s)	 To assess the effect of oral treprostinil on the following (assessed in all cohorts): Cardiopulmonary exercise testing (CPET) with progressive cycle ergometry Symptoms of PAH Panama functional classification WHO functional classification Six-minute walk distance (6MWD) (with oximetry and heart rate [HR] recovery monitoring) Borg dyspnea score Quality of life assessed via the Pediatric Quality of Life Inventory (PedsQLTM) questionnaire Plasma N-terminal pro-B-type natriuretic peptide (NT-Pro BNP) Cardiac magnetic resonance imaging (cMRI)
Study Design	Subjects with PAH aged 7 to 17 years. Multi-center, open-label, safety, tolerability and PK study of oral treprostinil in pediatric subjects with stable PAH aged 7 to 17 years who are, (1) transitioning from IV/SC Remodulin therapy; (2) transitioning from inhaled prostacyclin therapy; or (3) not currently receiving prostacyclin therapy.
Sample Size	Up to 40 pediatric subjects aged 7 to 17 years (25 transition [IV/SC Remodulin and inhaled] subjects and 15 de novo subjects)

Summary of	All Cohorts:
Subject Eligibility Criteria	Eligible subjects are between 7 and 17 years of age, inclusive, and have a diagnosis of PAH as confirmed by a previous right heart catheterization (RHC). Panama functional classification IIIb and IV subjects will be excluded.

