3.3.2.2 Vital Signs

Vital signs will be assessed during all study visits, including every day of the inpatient hospital stay (Cohort 1 subjects only). Vital signs measured will include blood pressure (BP, systolic and diastolic), HR, respiratory rate (RR), temperature (°C), and weight. Vital signs must be assessed following at least five minutes of rest (sitting) to ensure accurate measurement. No other measurements or procedures should be performed during this five-minute period. Vital signs will be collected prior to or after at least 30 minutes following the 6MWT. Vital signs should also be assessed in the case of abnormal clinical signs and symptoms. Height will be recorded at Screening.

3.3.2.3 12-Lead ECG

A 12-lead ECG will be recorded after at least five minutes rest in the semi-recumbent position at Baseline and repeated at Week 24/Premature Termination. Recordings should include lead II as a rhythm strip and contain at least five QRS complexes. The ECG parameters (after at least five minutes rest) include HR, PR interval, QT interval, QRS duration, and any clinically significant abnormalities.

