4.1 INCLUSION CRITERIA

A subject is eligible for inclusion in this study if all of the following criteria apply:

- 1. Legal guardian informed consent and subject assent, if appropriate, to participate in the study is voluntarily given.
- 2. The subject is between 7 and 17 years of age, inclusive, on the date informed consent is signed.
- 3. *Cohort 3:* The subject must weigh a minimum of 22 kg at Screening.
- 4. The subject has a current diagnosis of PAH (WHO Group I) associated with:
 - a. Idiopathic or heritable PAH
 - b. Persistent PAH for at least one year following surgical repair of a congenital systemic-to-pulmonary cardiac shunt, congenital heart disease, or other congenital heart lesions with no clinically significant residual defects and condition is stabilized hemodynamically
 - c. PAH in subjects with unrepaired restricted atrial septal defect, ventricular septal defect, or patent ductus arteriosus; subject must have a resting postductal oxygen saturation (off oxygen) of greater than 88%
- The subject has a current diagnosis of PAH confirmed by right heart catheterization (RHC) prior to the Screening visit with the following parameters:
 - a. Mean pulmonary arterial pressure (mPAP) of ≥25 mmHg
 - b. Pulmonary vascular resistance index (PVRi) of >3 Wood Units * m²
 - c. Left ventricular end diastolic pressure (LVEDP) or pulmonary capillary wedge pressure (PCWP) of ≤15 mmHg

- 6. Cohort 1: The subject must have been receiving IV/SC Remodulin for at least 90 days without dose change for at least 30 days prior to Baseline. The IV/SC Remodulin dose will be between 25-75 ng/kg/min, inclusive, for the first five subjects in the cohort. Following a safety review, the dose range may be expanded to 25-125 ng/kg/min, inclusive, for the remaining subjects. Subjects must be receiving stable doses of all other PAH medications for at least 14 days prior to the Baseline assessments; exception for diuretics and anticoagulants as outlined in Section 4.3.1.
- 7. Cohort 2: The subject must have been receiving inhaled prostacyclin for at least 90 days and has been at the current stable dose without changes for at least 30 days prior to Baseline. Subjects must be receiving stable doses of all other PAH medications for at least 14 days prior to the Baseline assessments; exception for diuretics and anticoagulants as outlined in Section 4.3.1.

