15.2 FUNCTIONAL CLASSIFICATION

PANAMA FUNCTIONAL CLASSIFICATION FOR CHILDREN AGED 5-16 YEARS

Class	Children with pulmonary hypertension
I	Asymptomatic, growing along own centiles, attending school regularly, no limitation of physical activity, playing sports with his/her classmates
II	Slight limitation of physical activity, unduly dyspnoeic and fatigued when playing when playing with his/her class- mates. Comfortable at rest. Continues to grow along own centiles. School attendance 75% normal. No chest pain
IIIa	Marked limitation of physical activity. No attempt at sports. Comfortable at rest. Less than ordinary activity causes undue dyspnoea, fatigue, syncope or chest pain. Schooling compromised, <50% normal attendance
IIIb	Unable to attend school, but mobile at home and interacting with friends. Wheelchair needed outside the home. Growth compromised. Poor appetite. Supplemental feeding. Less than ordinary activity (dressing) causes undue dyspnoea, fatigue, syncope and/or presyncope or chest pain. Plus features of Class IIIa)
IV	Unable to carry out any physical activity without undue dyspnoea, fatigue, syncope or chest pain, unable to attend school, wheelchair dependant, not interacting with friends. Syncope and/or right heart failure. Plus features of Class III

WHO FUNCTIONAL CLASSIFICATION FOR PH

Class I: Patients with pulmonary hypertension but without resulting limitation of physical activity. Ordinary physical activity does not cause undue dyspnea or fatigue, chest pain, or near syncope.

Class II: Patients with pulmonary hypertension resulting in slight limitation of physical activity. These subjects are comfortable at rest, but ordinary physical activity causes undue dyspnea or fatigue, chest pain or near syncope.

TDE-PH-206

Class III: Patients with pulmonary hypertension resulting in marked limitation of physical activity. They are comfortable at rest. Ordinary activity causes undue dyspnea or fatigue, chest pain, or near syncope.

Class IV: Patients with pulmonary hypertension with inability to carry out any physical activity without symptoms. These subjects manifest signs of right heart failure. Dyspnea and/or fatigue may be present even at rest. Discomfort is increased by any physical activity.

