### 11.6 VITAL SIGNS

Vitals signs (blood pressure [systolic and diastolic], heart rate, respiratory rate, and temperature [°C]) along with weight measurements will be captured during all study visits, including days of the inpatient hospital stay for Cohort 1. Height and body mass index were recorded at Screening only.

All vital sign assessments, including weight and height, will be listed by cohort, subject, and scheduled time point in chronological order using the units captured on the eCRF. Weight and height will be converted to a single unit for summarization; specifically, weight will be converted to kg and height will be converted to cm. The summary of vital signs will include descriptive statistics of the applicable parameters at each time point by cohort, including changes from Baseline.

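### The 24-week change in peak watts is compared with Baseline unscaled for body size, and peak VO2 has no stated unit, so in growing children without a control group growth cannot be separated from a treatment effect

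*SAP*

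**What the plan says.** SAP 10.2 lists three CPET variables for analysis of change: peak VO2, the VE/VCO2 slope and peak watts. The changes in peak VO2, the VE/VCO2 "slope, and peak watts will also be descriptively summarized. These changes will be compared within cohorts using a paired t-test". The same section adds that "p-values will be calculated for descriptive purposes; no formal hypothesis testing is planned".

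Peak watts is an absolute measure. For VO2 the section says only that "Cardiopulmonary exercise testing entails measurements of oxygen uptake" and other variables, without a unit. Protocol 3.3.1.1 gives no unit either. Neither document names scaling to weight, body surface area or a predicted value for any CPET variable.

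On population and design, inclusion criterion 2 (protocol 4.1) reads: "The subject is between 7 and 17 years of age, inclusive, on the date informed consent is signed". The protocol title calls the trial "A Multicenter, Open-Label, 24-Week, Uncontrolled Study".

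Weight is among the vital signs taken at every visit (protocol 3.3.2.2, SAP 11.6), so a Baseline and a Week 24 weight are already collected.

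**The concern.** A larger child can generally produce more absolute work and take up more oxygen. The protocol itself treats workload as dependent on size: section 3.3.1.1 sets the ramp by weight band. A child who grows over 24 weeks and is otherwise unchanged would therefore tend to show a higher peak in watts. No control arm is present to absorb that drift.

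Two readings are at stake. Protocol 1.4 expects improvement over Baseline in Cohorts 2 and 3, and growth imitates improvement. For Cohort 1 it expects that the benefit of infused therapy is maintained, and there growth can cover a real loss. The effect of oral treprostinil on CPET is a secondary objective (protocol 2.2, SAP 2.1.2), and protocol 1.1 presents CPET as a better reflection of functional status in children than the walk test alone. The table should therefore be readable on a scale that allows for size.

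**Working it through.** The documents give no power, effect size, SD or significance level for CPET, so there is no planned figure to reproduce. The check below is an illustration.

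**Inputs from the documents**
- Planned cohort size: 10 to 15 (SAP 6, protocol 10.2).
- Ramp of 5 W/min below 40 kg, designed to reach maximum work in 8 to 12 minutes (protocol 3.3.1.1).
- Illustrative weight: 35 kg, from the dosing examples in protocol 6.1.1. It is not an expected mean for this population.

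**Assumed, not in the documents**
- Weight gain over 24 weeks of 1, 2 or 3 kg.
- SD of the within-subject change of 10%, 15% or 20% of the Baseline value.
- Two-sided level 0.05.
- Constant watts per kg and no drug effect.

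**Step 1. Relative growth.** 1/35 = 2.9%; 2/35 = 5.7%; 3/35 = 8.6%.

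**Step 2. Shift in watts.** The design peak load below 40 kg is 5 × 8 = 40 W to 5 × 12 = 60 W. At constant watts per kg, growth alone adds:
- 1 kg: 40 × 1/35 = 1.1 W to 60 × 1/35 = 1.7 W
- 2 kg: 2.3 to 3.4 W
- 3 kg: 3.4 to 5.1 W

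**Step 3. Chance of a nominally significant increase.** The paired t statistic follows a noncentral t distribution with n − 1 degrees of freedom and noncentrality √n × drift / SD. The chance sought is that it exceeds the 97.5% point of the central t distribution. For n = 10, drift 2.9% and SD 20%, the noncentrality is 3.162 × 0.145 = 0.46 and the chance is 6.1%. For n = 15, drift 8.6% and SD 10%, it is 3.873 × 0.86 = 3.33 and the chance is 87.2%.

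| n | Drift | SD 10% | SD 15% | SD 20% |
|---|---|---|---|---|
| 10 | 2.9% | 12.8% | 7.9% | 6.1% |
| 10 | 5.7% | 36.4% | 18.9% | 12.5% |
| 10 | 8.6% | 67.8% | 36.7% | 22.9% |
| 15 | 2.9% | 18.1% | 10.4% | 7.6% |
| 15 | 5.7% | 53.8% | 27.8% | 17.6% |
| 15 | 8.6% | 87.2% | 54.3% | 34.2% |

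Without drift the value is 2.5% in every cell. A gain of only 0.5 kg (0.5/35 = 1.4%) gives 4% to 7%.

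**Step 4. Masking in Cohort 1.** If true watts per kg fall by 5.7% while weight rises by 5.7%, absolute watts change by the factor 0.943 × 1.057 = 0.997. The planned comparison would show almost no change.

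**Step 5. Per-kg scale.** If watts and weight both rise by the factor 1 + g, the ratio is unchanged. The growth drift is then zero under the constant-per-kg assumption, and the chance in Step 3 returns to 2.5%.

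**The case against.** The strongest reply is that these p-values are labelled descriptive, no level is set, SAP 8.2 states that no formal hypotheses are tested, and the primary objective is safety and tolerability. This stands as far as it goes. A reader might infer that the plan attributes normal growth to the drug; the documents make no such attribution. But the label does not remove the drift from the mean change, which is reported whatever happens to the p-value.

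A reader might also infer that peak VO2 is analysed unscaled. The documents do not show that. The unit is missing, so storage per kg is neither stated nor excluded, and the central specialist may set analysis settings (protocol 3.3.1.1). Only watts is shown to be unscaled. No growth effect is claimed for the VE/VCO2 slope.

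A third inference concerns height. Protocol 3.3.2.2 says "Height will be recorded at Screening", and SAP 11.6 says "Height and body mass index were recorded at Screening only". This does not block per-kg scaling, which needs only weight. Nor does it support a wider finding:
- For the cMRI indices, a height 2.8 cm out of date at 140 cm changes body surface area by about 1% (√(142.8/140) = 1.01), and the documents do not say how the central reader indexes.
- For the Panama classes, the wording "Asymptomatic, growing along own centiles, attending school regularly" does not specify height centiles, and nothing says investigators lack growth records.

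Two further objections stand. The size of the bias rests on assumptions, and CPET may be waived below 130 cm, so the number of pairs may fall short of the cohort size. With 8 pairs and 5% growth the chance is 23% at SD 10% and 13% at SD 15%. Also, per-kg values have their own weakness. Protocol 1.2.4 lists nausea and diarrhea among the drug's frequent adverse events, and protocol Table 9-1 lists weight loss, weight gain and edema as expected disease events. Weight loss would raise watts/kg and look like improvement; fluid gain would do the reverse. This argues against replacing the absolute values.

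**Conclusion.** The concern holds for peak watts, and conditionally for peak VO2. As written, SAP 10.2 reports and tests a change in watts that growth pushes upward, in children with no control group. The same applies to peak VO2 if it is held in absolute units. The missing unit is itself a gap for an analysed variable. Growth and treatment effect cannot be separated in these rows, and in Cohort 1 growth can hide a decline.

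The direction is firm; the size is not. The range of about 6% to 87% depends on assumed weight gain, assumed SD, the planned 10 to 15 subjects all giving pairs, and constant watts per kg. It should be read as showing that the drift can matter, not as an estimate for this trial. Confidence is moderate. The point affects the reading of a secondary endpoint and leaves the primary assessment of transition or initiation untouched.

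**What to change.** In SAP 10.2:
- State the unit in which peak VO2 is stored and summarised.
- Add the change from Baseline to Week 24 in watts/kg and in peak VO2 in mL/kg/min, each using the weight recorded at the same visit. Summarise and compare them with Baseline in the same way as the absolute values, which stay in the table.
- Show the weight change beside them, because weight loss, fluid retention and fat mass all move per-kg values.
- Add a note that growth affects the absolute changes.

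The cost is SAP wording, two more rows in the CPET table and a display of weight change. No new measurement is needed.
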